Treatment of Perianal Fistulas in Crohn's Disease with Injection of Freshly Harvested Autologous Adipose Tissue: A placebocontrolled and randomized study

Participants

Department of Hepatology and Gastroenterology, Aarhus University Hospital

Ph.d [name]

[name], MD

Ph.d [name]

Department of Surgery, Pelvic Floor Unit, Aarhus University Hospital, Aarhus

Ph.d [name]

[name] [name]

Gastrounit, Herlev Hospital

Ph.D [name]

[name]

Department of Abdominal Surgery, Odense University Hospital

[name], MD

Surgical Department, Køge Hospital

Ph.d [name]

Abdominalcenter K, Bispebjerg Hospital

[name]

Aim

To investigate the effects of injection of freshly harvested autologous adipose tissue in 140 patients with Crohn's Disease (CD) and complex perianal fistulas.

Primary endpoint

Number of patients who have achieve complete clinical healing 6 months after treatment with freshly harvested adipose tissue. Complete clinical healing is defined as i) if the patient has no symptoms of discharge; (ii) no visible external fistula opening in the perineum; (iii) no internal opening can be palpated with rectal digital examination (iv) no signs of a fluid conducting tract at the location of the former fistula.

Secondary endpoints

- a) Number of patients who have achieve complete clinical healing 3 months after treatment with freshly harvested adipose tissue.
- b) Number of patients with complete or partial healing 6 months after treatment.
- c) Reduction of symptoms evaluated by the Perianal Disease Activity Index (PDAI) 3 months after treatment.
- d) Reduction of symptoms evaluated by the Perianal Disease Activity Index (PDAI) 6 months after treatment.
- e) Changes in fecal inconsistency evaluated by St. Marks score

Background

Perianal fistulas are frequently present in Crohn's Disease (CD). The cumulative incidence of CD patients who develop perianal fistulas is as high as 26% during 20 years of follow-up, with the greatest risk present in the first 10 years after diagnosis.

Treatment of perianal fistulas with cultured mesenchymal stem cells derived from adipose tissue marrow has shown efficacy in CD patients. The use of cultured autologous cells, however, has the disadvantage of being time consuming, as it involves a harvesting procedure and weeks of *in vitro* stem cell expansion.

The injection of freshly harvested autologous adipose tissue is an easily accessible alternative to *in vitro* expanded autologous adipose-derived stem cells.

Present study investigate the effects of injection of freshly harvested autologous adipose tissue in 140 CD patients with complex fistulas.

Methods

Design

The study is a randomized double-blinded and placebo-controlled interventional study. It will be conducted as a national multicenter study. Based on a power-calculation 140 patients will be included. An interim analysis will be performed after the inclusion of 80 patients.

Patients

Inclusion Criteria

- a) Diagnosed with Crohn's Disease
- b) Perianal fistula with out branching or cavities with one external and one internal opening, which due to the risk for development of incontinence is not suitable for lay-open procedure, meaning: 1) all anterior interspinchteric and low transspinchteric (involving<1/3 of spinchter) in women 2) high interspinchteric fistulas 3) high

transsphincteric (>1/3 of sphincter), suprasphincteric and ekstrasphincteric fistulas 4) intersphincteric or low transsphincteric fistula in patients with fecal incontinence and/or fecal urge.

- c) no or minimal luminal disease activity by colonoscopy < 3 months before treatment defined by Simple Endoscopic Severity for Crohn's Disease<3
- d) Prior optimal medical treatment for fistulas (immunmodulators, antibiotics and/or anti-TNF-alfa treatment) with out achieving fistula healing
- e) Treatment with seton for a minimum of 6 weeks
- f) Speaks and understand Danish

Exclusion Criteria

- a) Pregnancy
- b) Changes in immunmodulator or anti-TNFalfa treatment < 12 weeks
- c) Anovaginal fistulas
- d) Rectal or anal stenosis
- e) Active proctitis
- f) Stoma
- g) Previous surgery for fistulas besides simpel drainage or seton
- h) Smoker
- i) Insulin-dependent diabetes, conditions inducing defective immunity, previous pelvic radiation
- j) pelvic MRI contraindicated

Study course

Included patients will in the period before treatment with freshly collected adipose tissue or placebo receive standard surgical (regular curettage and seton) and/or medical treatment for their fistula(s). When the treating surgeon estimates (reduced secretion and fistula shrinkage) that the patients can achieve fistula healing by injection with freshly collected adipose tissue patients will be referred to pelvic MRI for exact fistula classification. The patient will only be included if pelvic MRI confirms that the fistula is applicable for treatment with freshly collected adipose tissue.

The surgical procedure is performed in general anaesthesia. An abdominal liposuction will be performed and thereafter patients will be randomized 1:1 to either injection with freshly collected adipose tissue or saline (placebo). At least two experienced surgeons will be affiliated to the study at each study center. One will perform the surgical procedure and the other will be blinded for whether the patient receives active or placebo treatment. The blinded surgeon will be responsible for the subsequently clinical evaluations of the treatment effects. Clinical evaluation of the treatment response will be performed 3 months after the procedure. If healing has not been achieved the initial treatment (adipose tissue/placebo) will be repeated and the treatment response will be evaluated following another 3 months. Patients with clinical healing after 3 months will be evaluated again 6 months after treatment. In case patients also present clinical healing 6 months after treatment a pelvic MRI will be performed to confirm complete fistula healing. All pelvic MRI scans will be reviewed centrally and the evaluating radiologist is blinded to what treatment the patients have received. Placebo treated patients who do not achieve healing from 2 placebo treatments will subsequently be offered treatment with injection with adipose tissue. Patients who achieves fistula healing will be followed for a total of 2 years.

Patients who receive immunomodulators or biological treatment at the time for inclusion will continue this treatment in the study period. However, the treatment will be paused 2 weeks before and 3 weeks after treatment.

Surgical procedure

The surgical procedure will be performed as previously described (Gastroenterology 2019 Feb 14. pii: S0016-5085(19)30375-0. doi: 10.1053/j.gastro.2019.02.005. [Epub ahead of print]

Randomization

A randomizationlist has been generated by use of the webpage randomization.com The randomization will be performed en bloc (5 adipose tissue/ 5 placebo)

Statistical considerations

Data analysis will be performed as intention-to-treat. A power-calculation has shown a power of 80 % based on the assumptions that 55% of the patients receiving active treatment and 30 % of the patients receiving placebo achieves clinical healing 6 months after treatment with a level of 0.05 for significance, when including 60 patients in each group. We have chosen to include a total of 140 patients who will be randomized 1:1. An interim analysis will be performed after 80 included patients. In case this interim analysis demonstrates a clear and statistical significant effect of the treatment compared to placebo further inclusion in the study be terminated.

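### Does leaving the start of the 6-month clock unstated for re-injected patients undermine the primary endpoint?

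*Combined protocol and SAP*

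**What the plan says.** The Primary endpoint section counts "Number of patients who have achieve complete clinical healing 6 months after treatment with freshly harvested adipose tissue". Under Secondary endpoints, item a is "Number of patients who have achieve complete clinical healing 3 months after treatment with freshly harvested adipose tissue", item b is "Number of patients with complete or partial healing 6 months after treatment", and items c and d place the perianal activity index at 3 and 6 months after treatment. Statistical considerations ties the assumed healing rates of 55% and 30% to the same 6-month wording and specifies intention-to-treat analysis.

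Study course allows up to two blinded procedures. Everyone is first evaluated 3 months after the procedure. For patients not healed then, "the initial treatment (adipose tissue/placebo) will be repeated and the treatment response will be evaluated following another 3 months". For the others, "Patients with clinical healing after 3 months will be evaluated again 6 months after treatment". Imaging follows: "In case patients also present clinical healing 6 months after treatment a pelvic MRI will be performed to confirm complete fistula healing". Crossover comes last: "Placebo treated patients who do not achieve healing from 2 placebo treatments will subsequently be offered treatment with injection with adipose tissue". Finally, "Patients who achieves fistula healing will be followed for a total of 2 years".

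Nowhere is the procedure that starts the clock named.

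**The concern.** With up to two procedures about 3 months apart, 6 months after treatment has two possible meanings.

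- **Clock from the first procedure.** Everyone is read at about month 6. A second-procedure healer then counts as a success on a reading 3 months after that procedure, while a one-procedure healer has been followed for 6 months. The reported rate pools the two.
- **Clock from the last procedure.** Re-injected patients are due at about month 9, a visit that is not clearly scheduled.

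Secondary endpoints a to d and the confirmatory MRI share the unstated start. Endpoint a is the most sensitive, since a last-procedure clock would add second-round healers to it. If the choice were really open, it could be made after the data were seen, and a reader could not tell how much of the 6-month rate was 3-month healing.

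**Working it through.** **1. The plan's own figure.** Inputs from Statistical considerations: 55% against 30%, significance level 0.05 (taken as two-sided), 60 per group. Two-proportion z test with pooled null variance:

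- mean proportion = (0.55 + 0.30)/2 = 0.425
- SE under the null = √(2 × 0.425 × 0.575/60) = 0.0903
- SE under the alternative = √((0.55 × 0.45 + 0.30 × 0.70)/60) = 0.0873
- power = Φ((0.25 − 1.96 × 0.0903)/0.0873) = Φ(0.837) = 79.9%, against 80% stated

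At 70 per arm (140 patients, 1:1) the same formula gives 85.7%. Naming the first procedure as the start changes none of this.

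**2. The schedule, counted from the first procedure.**

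| Patient | First reading | Second procedure | Next reading | Time since last procedure |
|---|---|---|---|---|
| Healed at month 3 | month 3 | none | month 6 | 6 months |
| Not healed at month 3 | month 3 | about month 3 | 3 + 3 = about month 6 | 3 months |

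Both routes end at about month 6. Two further features fit this clock. The offer of adipose tissue to placebo patients follows failure of two placebo treatments, and the evaluation stated for judging that is the one 3 months after the second; a month-9 primary reading would fall after some placebo failures could already have crossed over. And if no healed patient relapsed, endpoint a on a last-procedure clock would equal the 6-month rate, leaving little reason to list it separately.

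**3. How large could the mixing be?** The documents give no month-3 healing rate and no relapse rate, so the following are assumptions. Let q be healing 3 months after the first procedure, kq the healing rate of a second procedure, and r the relapse between 3 and 6 months after a procedure, the same after either procedure and in both arms. Solve

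q(1 − r) + (1 − q)kq = 0.55 (active) or 0.30 (placebo).

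Second-procedure healers are (1 − q)kq. Healing 6 months after the last procedure is (q + (1 − q)kq)(1 − r). For k = 1 and r = 0, q = 1 − √0.45 = 0.329 and 1 − √0.70 = 0.163.

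| k | r | q, active / placebo | Re-injected of 140 | Second-procedure healers | Healed 6 months after last procedure | Power, 70 per arm |
|---|---|---|---|---|---|---|
| 0.5 | 0 | 0.428 / 0.215 | 95.0 | 14.5 | 0.550 vs 0.300 | 86% |
| 0.5 | 0.3 | 0.617 / 0.283 | 77.0 | 15.4 | 0.515 vs 0.270 | 85% |
| 1 | 0 | 0.329 / 0.163 | 105.5 | 25.0 | 0.550 vs 0.300 | 86% |
| 1 | 0.3 | 0.435 / 0.200 | 95.6 | 28.4 | 0.476 vs 0.252 | 79% |
| 2 | 0 | 0.214 / 0.108 | 117.5 | 37.0 | 0.550 vs 0.300 | 86% |
| 2 | 0.3 | 0.250 / 0.122 | 113.9 | 41.3 | 0.438 vs 0.236 | 72% |

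The count of second-procedure healers nearly triples across the table, driven mainly by k, on which the documents are silent. The last two columns apply only if the less natural clock were used; without relapse they do not move.

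**4. Endpoint a.** With k = 1 and r = 0 it is 33% vs 16% from the first procedure and 55% vs 30% from the last. The first evaluation takes place in every patient before any re-injection, so the first-procedure figure is the ordinary one.

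**The case for a change.** The strongest reply is that a clear implication is still only an implication. Intention-to-treat fixes the arm in which a patient is counted, not the date of the reading. Even on the natural clock, a substantial share of successes may have only 3 months behind them, and with k = 1 and r = 0 endpoint a differs by 22 points in the active arm between the two readings. A clause naming the first procedure, a split of successes by number of procedures, and a later reading for second-procedure healers would seem cheap.

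Part of this stands. The start is not written down, and a report should say that two-procedure healers were read about 3 months after their last procedure. The date of the MRI for those patients is also unstated, but the primary endpoint consists of four clinical criteria without MRI, so it does not alter who counts as a success.

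The rest does not carry. The split by number of procedures describes subsets formed after randomisation and changes no primary result. A month-9 reading asks a different question, durability after the last procedure. It may also need a new visit, because the 2-year follow-up is given no start and no visit dates. Its benefit rests on relapse and second-procedure rates that nobody has supplied.

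**Conclusion.** This is a gap in wording that analysts would fill sensibly, and it needs no change to the plan. The schedule brings one- and two-procedure patients to a reading about 6 months after the first procedure. At that point both arms have followed the same retreatment rule under blinding and placebo crossover has not begun, so the randomised comparison of a strategy of up to two procedures is valid. The stated power reproduces and is unaffected.

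Pooling 3 and 6 months since the last procedure is a property of that strategy, not an error. If the last-procedure clock were used instead, the assumed difference of 25 points would shrink to between 25 and 20 points, and power at 70 per arm would lie between 86% and 72%. That range depends on a second procedure 0.5 to 2 times as effective as the first and relapse of 0 to 30%, none of which the documents give. The conclusion also assumes that re-injection takes place close to the month-3 visit, as Study course implies.

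### Does counting the interim by 80 included patients, with no stated data cut-off, leave the interim analysis undefined?

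*Combined protocol and SAP*

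**What the plan says.** The interim is defined in two places. Methods, Design: "An interim analysis will be performed after the inclusion of 80 patients". Statistical considerations: "An interim analysis will be performed after 80 included patients". Neither adds a follow-up condition. If the effect at that look is both clear and statistically significant, the consequence is "further inclusion in the study be terminated". No interim significance level is given.

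The primary endpoint is complete clinical healing 6 months after treatment. The power statement uses the same time point: "achieves clinical healing 6 months after treatment with a level of 0.05 for significance".

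Inclusion is used in three ways:
- Study course, before the MRI: "Included patients will in the period before treatment with freshly collected adipose tissue or placebo receive standard surgical".
- Study course, at the MRI: "The patient will only be included if pelvic MRI confirms that the fistula is applicable for treatment with freshly collected adipose tissue".
- Statistical considerations, as the randomised total: "We have chosen to include a total of 140 patients who will be randomized 1:1".

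Randomisation itself takes place during the operation: "An abdominal liposuction will be performed and thereafter patients will be randomized 1:1".

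**The concern.** With a 6-month endpoint, the most recently treated patients cannot have an outcome on the day the 80th patient is included. The wording fits a test on that day, using whatever outcomes exist, and equally a test once all 80 have passed month 6. These are different samples and can give different stopping decisions. The loose use of inclusion adds to this. If patients are counted before the MRI, 80 included is not 80 randomised, and the lag before treatment adds to the number without an outcome.

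At stake would be a trial that continues, or stops, because of an unplanned choice of cut-off, and a stopping boundary that cannot be calculated because the information fraction is unknown.

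**Working it through.** **Inputs from the plan.** Healing 55% against 30%, significance level 0.05, 60 per group for 80% power, 140 randomised 1:1 (70 per group), interim at 80, outcome at 6 months.

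**Assumptions.** Two-sided test; 1, 2, 4 or 6 patients per month; inclusion counted at treatment; p<0.05 as the interim trigger. The plan states none of these.

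**Step 1: reproduce the plan's figure.** With n per group, power = Φ[(0.25√n − 1.96·s₀)/s₁], where
- s₀² = 2 × 0.425 × 0.575 = 0.48875, so s₀ = 0.699;
- s₁² = 0.55 × 0.45 + 0.30 × 0.70 = 0.4575, so s₁ = 0.676.

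At n = 60: (1.937 − 1.370)/0.676 = 0.837, power 79.9%. The stated 80% is reproduced. At n = 70 power is 85.7%.

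**Step 2: interim power by cut-off.** Pending patients = 6 × monthly accrual; evaluable = 80 − pending. With all 80 evaluable (n = 40): (1.581 − 1.370)/0.676 = 0.312, power 62.2%.

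**Step 3: how often the cut-offs disagree.** The test at the evaluable number and the test at 80 are treated as bivariate normal with correlation √(evaluable/80). A late-only result is one significant with all 80 but not at the early cut; early-only is the reverse.

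**Step 4: effect on the whole trial.** The interim and the final test at 140 are treated as bivariate normal with correlation √(evaluable/140), using 0.05 at both looks. Two-look power and type I error are the chance that at least one test is significant.

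| Accrual per month | Evaluable | Interim power | Late-only | Early-only | Disagree | Two-look power | Two-look type I error |
|---|---|---|---|---|---|---|---|
| wait for all | 80 | 62.2% | – | – | – | 87.3% | 8.1% |
| 1 | 74 | 58.8% | 6.2% | 2.8% | 9.0% | 87.2% | 8.2% |
| 2 | 68 | 55.1% | 10.4% | 3.3% | 13.6% | 87.2% | 8.4% |
| 4 | 56 | 47.2% | 18.5% | 3.5% | 22.0% | 87.1% | 8.6% |
| 6 | 44 | 38.5% | 27.1% | 3.3% | 30.4% | 86.9% | 8.9% |

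Most disagreements are late-only: the early look does not stop and the trial goes on towards 140. That is why overall power moves by only 87.3 − 86.9 = 0.4 points. Type I error moves by 8.9 − 8.1 = 0.8 points; the other 8.1 − 5.0 = 3.1 points are present even when all 80 are evaluable, so they come from testing twice without a boundary.

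**Step 5: is waiting better?** Expected patients saved by stopping, at 4 per month with inclusion continuing while the result is awaited (24 of the remaining 60 enter meanwhile):
- Unadjusted 0.05: early cut 0.472 × 60 = 28.3; waiting 0.622 × 36 = 22.4.
- O'Brien-Fleming-type spending (an illustration, not in the plan): early cut 0.106 × 60 = 6.4; waiting 0.366 × 36 = 13.2.

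The preferred cut-off reverses with the boundary, so neither is right in itself.

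**Step 6: the inclusion wording.** No arithmetic applies here, because every figure above counts inclusion at treatment. A patient who is never randomised has no arm and cannot enter a comparison of adipose tissue with saline. The sentence on 140 patients ties inclusion to 1:1 randomisation, and the interim sentence follows directly. Read in order, the 80 are the first 80 of the 140. The contrary evidence is one loosely worded sentence about the preparatory period, which the MRI condition later in the same paragraph already contradicts.

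**The case for a change.** The strongest case for a change is that, without a written cut-off, the interim sample could be chosen after outcomes have begun to accumulate, and that no spending boundary can be fixed in advance. With O'Brien-Fleming-type spending the interim p threshold is 0.0095 at 80 evaluable and 0.0005 at 44, a large difference. A short paragraph would remove the doubt.

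The facts behind this stand: no cut-off is stated, inclusion is worded inconsistently, and that an analyst would wait for month 6 is a judgement about ordinary practice, not something the text says. The dependence of the threshold on information also stands, but it arises only once a spending boundary has been chosen, and the plan has none. Anyone writing that boundary must fix the information fraction to compute it, so the cut-off is settled there.

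The disagreement rates carry less weight than they seem to. They rest on an assumed accrual rate, which alone produces the range from 9.0% to 30.4%, and on p<0.05 as the trigger, although the plan asks for an effect that is clear as well as significant. An instruction to wait would also need a missing-outcome rule for the interim, and the plan gives none beyond intention-to-treat.

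**Conclusion.** No change to the plan follows from this point. The missing cut-off is a gap that the 6-month endpoint and power statement lead an analyst to fill sensibly, and the choice between an early and a complete interim is a fair trade-off. The inconsistent use of inclusion is a wording slip, with no effect calculated here, and the sample-size sentence largely resolves it.

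Under the plan's own healing rates, with assumed accrual of 1 to 6 per month and 0.05 at both looks, the cut-off changes overall power by at most 0.4 points and type I error by at most 0.8 points. Its effect on the stopping decision can be larger: up to 30.4% disagreement at 6 per month, but 9.0% at 1 per month. The absence of a stopping boundary is the more consequential matter and stands apart from this one.

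### Does it undermine the primary result that the month-6 MRI may not reach patients who heal only after the repeat injection?

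*Combined protocol and SAP*

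**What the plan says.** The Primary endpoint section sets the outcome as "Number of patients who have achieve complete clinical healing 6 months after treatment with freshly harvested adipose tissue". It defines healing by absence of discharge, of a visible external opening, of a palpable internal opening and, as criterion (iv), "no signs of a fluid conducting tract at the location of the former fistula". MRI is not mentioned there or in secondary endpoints a to e.

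The Study course section gives two routes after the 3-month visit:

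- Not healed: "If healing has not been achieved the initial treatment (adipose tissue/placebo) will be repeated and the treatment response will be evaluated following another 3 months". No scan is mentioned.
- Healed: "Patients with clinical healing after 3 months will be evaluated again 6 months after treatment". The next sentence is the MRI sentence: "In case patients also present clinical healing 6 months after treatment a pelvic MRI will be performed to confirm complete fistula healing".

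Scans are read centrally by a radiologist blinded to treatment. MRI is also used at entry ("The patient will only be included if pelvic MRI confirms that the fistula is applicable"), and the exclusion list includes "pelvic MRI contraindicated".

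Statistical considerations specifies an intention-to-treat analysis. It bases power on clinical healing at 6 months in 55% of active and 30% of placebo patients, and refers to no imaging result.

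**The concern.** In the MRI sentence the word *also* most naturally points back to patients healed at 3 months. A patient who fails the first injection, is re-treated and is healed when "the treatment response will be evaluated following another 3 months" then gets no scan. If the 6 months run from the first injection, that patient is still a primary success.

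Two things would seem to be at stake. First, whether a healer is scanned would depend on response to the first injection. That is a post-randomisation event whose frequency can differ by arm, so MRI-confirmed healing could not be set beside the primary count. Second, criterion (iv) names no method of assessment. If MRI could overturn the surgeon's finding, healers after one injection would face a stricter test than healers after two. The protocol does not say how to classify a patient who is clinically healed but has a tract on MRI.

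**Working it through.** **1. Does any planned result use the MRI?**

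| Element | Basis | MRI used? |
|---|---|---|
| Primary endpoint | four clinical criteria, 6 months | no |
| Secondary a, b | complete, or complete or partial, healing | no |
| Secondary c, d | PDAI | no |
| Secondary e | St. Marks score | no |
| Power and analysis | clinical healing, 55% vs 30% | no |

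The stated power is reproduced from clinical rates alone. With pooled variance and two-sided 0.05 (the sidedness is assumed), z = [d√n − 1.96√(2p̄q̄)] / √(p₁q₁ + p₂q₂).

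- Inputs: d = 0.25, p̄ = 0.425, 2p̄q̄ = 0.48875, p₁q₁ + p₂q₂ = 0.4575.
- n = 60 per group: z = (1.936 − 1.370)/0.676 = 0.837, power 79.9% against the stated 80%.
- n = 70 per group (140 in all): z = (2.092 − 1.370)/0.676 = 1.067, power 85.7%.

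Neither figure depends on who is scanned.

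**2. Can criterion (iv) be an MRI finding?** The scan is ordered once clinical healing at 6 months has been found. Criterion (iv) is part of that finding, so it has to be judged before the scan. The endpoint's name and the blinded surgeon's responsibility for clinical evaluation point the same way.

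**3. Who is scanned under each reading?**

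- A. Clock from the first injection, *also* meaning healed at both visits: re-treated healers are not scanned.
- B. Clock from the first injection, sentence loosely meant for every month-6 healer: all are scanned.
- C. Clock restarting at re-treatment. The sentence on patients healed after 3 months comes after the re-treatment sentence and is not limited to the first injection. It can cover anyone healed 3 months after either injection, who is then seen 6 months after that injection: all are scanned.

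The text does not decide between these.

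**4. Size under reading A (illustration only).** Expected healers: 70 × 0.55 = 38.5 and 70 × 0.30 = 21, total 59.5. Let p be the chance of healing after the first injection and k the ratio of second- to first-injection success. Assume no relapse, the same k in both arms, k between 0 and 1, and that 55% and 30% include healing after re-treatment. Then p + (1 − p)kp equals the month-6 rate. Unscanned healers per arm are 70 × (month-6 rate − p).

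| k | p active | p placebo | unscanned | share of 59.5 | scanned difference |
|---|---|---|---|---|---|
| 1 | 32.9% | 16.3% | 15.5 + 9.6 = 25.0 | 42% | 16.6 points |
| 0.5 | 42.8% | 21.5% | 8.6 + 5.9 = 14.5 | 24% | 21.2 points |
| 0.25 | 48.8% | 25.3% | 4.4 + 3.3 = 7.7 | 13% | 23.5 points |
| 0 | 55% | 30% | 0 | 0% | 25 points |

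The last column assumes that MRI agrees with every clinical call and that unscanned healers count as not confirmed.

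**5. Is the shrinkage general?** No. Keep the totals at 55% and 30%, but suppose 50% + 5% in the active arm and 20% + 10% on placebo (first plus second injection). The scanned difference is 50 − 20 = 30 points, more than 25. The direction depends on the assumption of equal k.

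**The case for a change.** The best case for acting is practical. Patients are treated at five hospitals, and surgeons at each must apply this sentence. If they read it differently, some healers are scanned and others are not, and a scan missed at month 6 cannot be recovered. This is the trial's only imaging check on a surgeon's judgement, and it is read blinded and centrally. Clarifying it would take two or three sentences. Scanning looks feasible, since MRI is needed for entry and a contraindication excludes.

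Part of this stands. The sentence is ambiguous, and on reading A the imaging data would cover a selected subset of healers. Which injection starts the 6-month count is also not stated. That is a separate question, which the scan schedule neither creates nor resolves.

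The step from there to a flaw in the plan does not stand. The distorted arm difference and the comparison of post-randomisation subgroups arise only in an MRI-confirmed comparison by arm, which the protocol does not plan. On reading A, scanning re-treated healers would mean extra procedures for data that enter no listed endpoint. Rules for reporting such a comparison would govern an analysis that nobody has proposed.

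**Conclusion.** No change to the plan is needed. The primary comparison, the five secondary endpoints, the sample size and the significance level are the same whether re-treated healers are scanned or not. Healers after one injection and after two are both counted on clinical findings alone. This rests on criterion (iv) being a clinical judgement, which the order of events supports.

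The number of healers who might go unscanned cannot be taken from the documents. It is zero under readings B and C. Under reading A with the assumed model it lies between zero and about 25 of 59.5. The 16.6 and 21.2 point differences, with power of 0.63 and 0.77 at 70 per arm, describe an unplanned endpoint and should not be read as a loss to this trial.

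The residue is a gap in drafting that sensible practice fills: the trial team settles who is scanned, and the report says which healers had an MRI and presents the scans as supporting description.

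### Optional improvement: the primary comparison could be stratified, at little cost, by the MRI fistula class known before randomisation; the power gain is about 0 to 6 points, depending on an unknown prognostic effect

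*Combined protocol and SAP*

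**What the plan says.** All references are to the combined protocol and SAP.

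- **Statistical considerations.** The analysis is described by "Data analysis will be performed as intention-to-treat". The sample size rests on this assumption: "55% of the patients receiving active treatment and 30 % of the patients receiving placebo achieves clinical healing 6 months after treatment". It uses a 0.05 significance level and 60 per group to reach 80% power. The trial will enrol 140 patients, 1:1, with an interim analysis at 80 that may end inclusion. No test, stratification factor or covariate is named for the primary endpoint.
- **Inclusion Criteria, b.** Entry covers several kinds of tract. Some are low, such as "all anterior interspinchteric and low transspinchteric" tracts in women, and low tracts in patients with incontinence or urge. Others are high: high intersphincteric, high transsphincteric, "suprasphincteric and ekstrasphincteric fistulas".
- **Study course.** Before inclusion, "patients will be referred to pelvic MRI for exact fistula classification", and a patient enters only if the MRI confirms suitability. Randomisation comes later, during surgery, after the liposuction. All MRI scans are also reviewed centrally by a blinded radiologist.
- **Randomization.** Blocks of five active and five placebo, with no stratification factor stated.

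**The concern.** Each randomised patient has an anatomical class recorded before allocation, so treatment cannot affect it. Neither the allocation nor the stated analysis uses it. If low and high tracts heal at different rates, two things follow:

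- A chance difference in class mix between arms moves the observed healing difference. Such differences are most frequent at the 80-patient look, where the trial may stop.
- An unstratified comparison carries between-class variation that a stratified one removes, so some precision is left unused.

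If an imbalance appears and no adjusted analysis was fixed beforehand, any later adjustment is post hoc and open to challenge.

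**Working it through.** **1. Reproducing the plan's figure.** Inputs from Statistical considerations: p1 = 0.55, p0 = 0.30, alpha 0.05 (sidedness not stated; taken as two-sided), n = 60 per group. With mean rate 0.425,

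z = [0.25·√n − 1.96·√(2·0.425·0.575)] / √(0.55·0.45 + 0.30·0.70) = [0.25·√n − 1.370] / 0.676.

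- n = 60: z = (1.936 − 1.370)/0.676 = 0.84, power 79.9%. The stated 80% is reproduced.
- n = 70 (planned): z = (2.092 − 1.370)/0.676 = 1.07, power 85.7% (85.6% by exact chi-square calculation).

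These powers ignore dropout and any alpha spent at the interim; the plan specifies neither.

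**2. What stratifying can remove.** The documents give no class mix and no healing rate by class. *Assumption:* half the patients in each class, and healing lower in one class by a gap g in both arms, with arm averages kept at 55% and 30%. Within-class variance per patient falls by g²/4 in each arm, so the variance of the risk difference falls by about (g²/2)/0.4575. For g = 0.30 that is 0.045/0.4575 = 9.8%. Estimating within strata gives back about 0.8%, leaving about 9%.

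**3. Simulation.** At least 200,000 trials per setting, uncorrected chi-square against Cochran-Mantel-Haenszel (CMH), class not balanced by design:

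| Gap (points) | Variance change, 70/arm | Power change, 70/arm (points) | Power change, 40/arm (points) |
|---|---|---|---|
| 0 | +0.8% | -0.2 | -1.4 |
| 10 | -0.5% | +0.2 | -1.2 |
| 15 | | +0.7 | -0.8 |
| 20 | -3.6% | +1.4 | 0.0 |
| 30 | -8.9% | +3.3 | +2.5 |
| 40 | -16.8% | +5.9 | |

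Unstratified power is about 85.6% at 70 per arm and 64.0% at 40 per arm. With a 70/30 split and a 30-point gap, variance falls 7.6% and power is about 88.3%. Two-sided type I error of CMH is 4.9% to 5.1%.

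**4. Number of classes.** A second parametrisation used a common treatment odds ratio and a prognostic odds ratio (OR) for class. With two equal classes at 70 per arm, the change is -0.2 points at OR 1, +0.7 to +0.8 at OR 2, +2.1 at OR 3 and +5.2 to +5.3 at OR 6. With four equal classes (OR between the extremes) it is -0.7 at OR 1, -0.2 at OR 2 and +2.6 at OR 6. Few classes are better.

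**5. Chance imbalance.** With half the patients in each class, the class share differs between arms by 10 points or more in 27% of trials at 70 per arm and 43% at 40 per arm. With a 30-point gap, a 10-point imbalance shifts the observed difference by 0.10 × 30 = 3 points. The standard error of that difference at 70 per arm is √(0.4575/70) = 8.1 points, so the shift is about 0.4 of a standard error.

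**The case against.** The strongest objection is that the premise is not in the documents. Nothing says that class predicts healing, how strongly, or in which direction. Entry is also narrowed to unbranched tracts with one opening at each end, in patients whose surgeon already expects healing, which could flatten any difference. A 40-point gap would mean placebo healing of 50% v 10%, an odds ratio of (0.5/0.5)/(0.1/0.9) = 9, and no passage supports that. This stands: the gain is conditional, and its lower end is about zero.

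Three stronger readings are tempting and should be resisted.

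- *The plan chose an unadjusted analysis and ignores class.* The text names no test at all, and the sentence on intention-to-treat concerns which patients are analysed. This is an omission, and the missing test is the larger gap.
- *Stratifying is free and assures at least a point of power.* A gain of one point needs a healing gap of nearly 20 points. At the 80-patient look the test loses power below a 20-point gap.
- *Without stratification the comparison is invalid or the trial underpowered.* Chance imbalance is already reflected in the unadjusted standard error, the unadjusted test is valid under randomisation, and 70 per arm exceeds the plan's own power target.

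The strata also need care. Intersphincteric tracts can be high, and criterion b admits anterior ones in women without stating their height. A simple split by name would therefore put some tracts in both classes.

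What survives is the uneven trade-off at 140 patients: a loss of about 0.2 points if class is irrelevant, against several points if it matters, plus protection from a post hoc argument over adjustment.

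**Conclusion.** The point holds as a cheap, optional improvement. The documents establish that class is known before randomisation for each patient, that entry mixes low and high tracts, and that neither allocation nor analysis is stated to use class. A two-class stratified test is valid and keeps type I error near 5%.

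Its value is about 0 to 6 points of power at 70 per arm, for healing gaps of 0 to 40 points with an even class split. The documents neither support nor contradict any value in that range. At the interim look the effect may be a loss.

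**What to change.** Add to Statistical considerations:

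*The primary comparison at the final analysis is the Mantel-Haenszel risk difference in complete clinical healing at 6 months, with 95% confidence interval and the Cochran-Mantel-Haenszel test, stratified by two classes from the pre-randomisation MRI. High: high intersphincteric, high transsphincteric, suprasphincteric or extrasphincteric. Low: every other eligible tract. The unadjusted comparison is reported as a sensitivity analysis.*

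Also state:

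- that the class is fixed for each patient before unblinding, and whether the local or the central MRI reading sets it;
- how a patient with more than one tract is classed, since Study course allows for a plural;
- which test is used at the 80-patient look, given the loss shown there when the healing gap is below 20 points.

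Cost: wording only, with no extra patients, visits or data. If class proves irrelevant, about 0.2 points of power are lost at 140 patients, and about 1.4 points at the interim if the same test is used there.
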